**Randomization**

Consented patients will be randomized into two groups at a 1:1 ratio using block permutations of 2 and 4. Randomization will be done using either an online randomization service or envelope system. Randomization will occur following the patient's consent into the study, either at the initial visit or the day of the planned injection. Once the randomization number is obtained, unblinded research staff will prepare the appropriate study drug. The injections will be blinded to the research coordinator in charge of data entry, the treating physician and the patient. Clinical staff will prepare the study drug injection and maintain the blind by placing a blank label over the syringe to ensure that the treatment is blinded to the patient and treating physician. Once a patient has been randomized, they become an enrolled subject and will be included in the intention to treat analysis of the trial outcomes, regardless of whether or not they receive study drug.

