**Screening and Enrollment**

Patients will be screened and consented at the University of Utah Orthopedic Center and all participating sub-investigator's clinics when they come for a standard of care physical exam. During this exam, the patient will be asked about their health and lifestyle, medical history, and current medications. As part of the SOC physical exam, the patient will also have standard of care pre-treatment x-rays, neurological assessment, and a diagnosis of mild to severe OA in the knee joint assessment. The patient will also complete standard of care questionnaires including pain assessment and outcome surveys which are described below:

- Pain will be measured by the Visual Analog Scale for pain (VAS Pain). VAS Pain is a patient-reported measurement tool used to quantify perceived level of pain, graded on a scale from 0 to 10 with 0 representing no pain and 10 representing the worse pain possible, and with precise measurement of the marked pain level's distance from 0 comprising the pain level.
- Functional outcomes will be assessed using Single Assessment Numerical Evaluation (SANE), PROMIS Physical Function CAT (PF CAT), and Knee Injury and Osteoarthritis Outcome Score (KOOS) scoring scales.
  - The SANE asks the patient to evaluate their percentage of normal on the affected joint or region of interest. This is a one-question survey with a scale from 0-100%.
  - The PFCAT is a bank of 160 questions related to physical function. It is a computerized adaptive test that asks the patient to self-report capabilities rather than actual performance of physical activities. It includes functioning of upper extremities, lower extremities, and central regions. It also assesses instrumental activities of daily living, such as running errands.

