**Study Drug Administration**

Study Drug Administration will only occur at the Orthopedic Center. Patients that are screened and consented at participating sub-investigator clinics will need to go to the Orthopedic Center to receive study drug. Patient eligibility will be reviewed prior to study drug administration. The standard of care

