**DATA COLLECTION**

Patients will be evaluated at baseline in the clinic. At 1 month after the injection an in-person clinic follow-up visit will occur. At this visit, concomitant medications, pain assessment, and outcomes will be assessed, as well as a physical exam and review of adverse events. Three, six and twelve months post injection, research staff will send an email/text to patients with a link to the surveys. If patients do not complete surveys within a week, research staff will follow up with a phone call to the patients inquiring about their knee(s) and instruct them to complete the various assessment tools online (VAS, SANE, PFCAT, and KOOS). Research staff may call patients after they complete surveys to clarify any responses. Information about repeat injections will be collected, including date of injection. Additional visits, which include a physical exam, review of concomitant medications and adverse events, will be done as needed.

Medical history, concomitant medications and physical exam will be collected at the baseline visit, prior to randomization. Concomitant medications will also be collected at the following time points: 1, 3, 6 and 12 months. Adverse events will also be collected at all follow-up time points (1 day, 2 days, 1 month, 3 months, 6 months and 12 months after baseline).

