**Time Period for Adverse Events**

For purposes of this study, events that occur following randomization through the last follow-up visit at 12 months will be reported as adverse events. Serious adverse events, unexpected medically attended events, and new onset chronic illnesses will be recorded from randomization through twelve months after the last study dose. Specifically, events that occur following informed consent to participate in the study, but prior to actual randomization, are not adverse events. These should be recorded as baseline conditions.

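### Randomisation may precede the injection day and the pre-injection eligibility review, so avoidable untreated patients can enter the ITT set, and the 6-month primary window has no stated start

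*Combined protocol and SAP*

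**What the plan says.** Under Randomization, allocation follows consent and may take place "either at the initial visit or the day of the planned injection". A randomised patient counts as enrolled and "will be included in the intention to treat analysis of the trial outcomes, regardless of whether or not they receive study drug".

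Under Screening and Enrollment, "Patients will be screened and consented at the University of Utah Orthopedic Center and all participating sub-investigator's clinics". Study Drug Administration confines injection to the Orthopedic Center, so patients from the other clinics "will need to go to the Orthopedic Center to receive study drug". The same section adds: "Patient eligibility will be reviewed prior to study drug administration". It does not say whether this review comes before or after randomisation.

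Time is counted in several ways:

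- **Primary Endpoint:** rescue medication received within 6 months, with no starting date given.
- **Data Collection, clinic visit and surveys:** 1, 3, 6 and 12 months counted from the injection.
- **Data Collection, adverse-event time points:** 1 day up to "12 months after baseline".
- **Patient Study Calendar:** the Day 1 and Day 2 contacts are set in hours from injection. Randomisation and drug administration share one Screening/Baseline column.
- **Time Period for Adverse Events:** "events that occur following randomization through the last follow-up visit at 12 months will be reported as adverse events". For serious events, recording runs from randomisation to twelve months after the last dose.

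**The concern.** When randomisation and injection fall on different days, patients can be lost to treatment in between. Eligibility is checked once before consent, but that check cannot catch later changes, such as an injection elsewhere, suspected infection at the injection site or recent surgery, all of which are exclusion criteria. Patients may also withdraw or not attend. Keeping them in the ITT analysis is right. The avoidable part is the gap that creates them.

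Two things are at stake. First, untreated patients can pull the two arms together on the primary endpoint. That endpoint is scored on receipt of a standard-of-care injection, so an untreated patient's first such injection could count as a repeat one. Second, the different origins agree only if randomisation and injection share a day. If they do not, the 6-month window could start on either date. For a patient never injected there is no injection date from which to count.

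**Working it through.** **Inputs.** From Sample Size Calculations and Statistical Power: 50% of SOC patients and 10% of pAF patients need a repeat injection by 6 months; 30 per arm; about 90% power; no stated allowance for untreated patients. From Data Analysis: Fisher's exact test, alpha 0.05, missing data not imputed. Sidedness is not stated, so I take two-sided. The number untreated (k per arm) and their event rate (q) are my assumptions, because the documents give neither.

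**Step 1: the plan's own figure.** Exact enumeration of the two-sided Fisher test, 30 v 30, 0.50 v 0.10, gives 91.4%. This agrees with the stated figure. The smallest size reaching 90% is 29 per arm, so the margin is one patient per arm.

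**Step 2: untreated patients who are followed up.** The ITT rate in an arm is

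(1 − k/30) × treated rate + (k/30) × q.

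With q = 0.50 the SOC rate stays at 0.50. The pAF rate becomes:

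- k = 1: (29/30) × 0.10 + (1/30) × 0.50 = 0.113
- k = 2: (28/30) × 0.10 + (2/30) × 0.50 = 0.127
- k = 3: (27/30) × 0.10 + (3/30) × 0.50 = 0.140

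With q = 0 both rates shrink by (30 − k)/30, giving 0.483 v 0.097, 0.467 v 0.093 and 0.450 v 0.090.

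**Step 3: untreated patients who are also missing.** If they provide no 6-month outcome and are lost equally from both arms, the rates stay at 0.50 v 0.10 and the sizes fall to 29, 28 or 27 per arm.

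**Results: two-sided Fisher power**

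| Untreated per arm | q = 50% | q = 0% | Missing equally |
|---|---|---|---|
| 0 | 91.4% | 91.4% | 91.4% |
| 1 | 88.4% | 89.8% | 90.0% |
| 2 | 84.9% | 88.0% | 89.1% |
| 3 | 80.9% | 86.1% | 87.3% |

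**Step 4: the clocks.** Suppose a patient is randomised at the initial visit and injected g days later. Adverse-event recording opens g days before the injection, while surveys run from the injection. The adverse-event assessments run from baseline, which is not tied to either date. The 6-month primary window could close on either of two dates g days apart. With g = 0 all of these agree. No dropout assumption is needed for this part.

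**The case against.** The strongest reply is that the protocol can be read coherently. The calendar puts consent, randomisation and drug administration in one column, and Randomization goes straight from obtaining the number to preparing the drug. On that reading, the initial-visit option is for patients injected at that visit, and the other option is for those who return or travel. This is plausible, but the text does not require it: it names the initial visit and the injection day as alternatives, and one calendar column is not a same-day rule.

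Several stronger readings are tempting and are not supported:

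- **That patients are randomised at sub-investigator clinics.** The text permits this but does not state it. Those clinics are named only for screening and consent.
- **That Data Collection times the follow-up visits from baseline.** It times the clinic visit and surveys from the injection; only the adverse-event time points are counted from baseline.
- **That events before injection enter the injection-related safety endpoint.** Exploratory Endpoints limits that endpoint to treatment-emergent events directly related to the injection. Recording from randomisation is a collection rule.
- **That the trial will lose ten points of power.** 80.9% is the low end of an assumed range. Patients who withdraw or do not attend may well have no 6-month outcome, which points to the milder missing-data column. With one untreated patient per arm, power is still close to the stated figure.

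It is also fair to say that randomising on the injection day does not remove every untreated patient. Someone not injected because of a suspicious aspirate stays in follow-up and in ITT by design, and a first standard-of-care injection for that patient would still score as an event.

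**Conclusion.** The point holds as a gap in the design text with a cheap remedy. The plan allows randomisation before the final eligibility review and before the injection day, which exposes the ITT set to avoidable untreated patients. It also leaves the origin of the primary window undefined.

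The stated power is sound on its own inputs. For 1 to 3 untreated patients per arm, the loss from 91.4% runs from 1.4 points (one per arm, missing equally) to 10.5 points (three per arm, 50% event rate). These are scenarios; the documents give no basis for choosing among them or for saying how many patients would be randomised early. The undefined origin does not depend on them, though it has practical effect only when randomisation and injection are on different days or the patient is never injected.

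**What to change.** In Randomization, replace the choice of two occasions with: *Randomisation takes place at the Orthopedic Center on the day of the planned injection, after the pre-injection eligibility review.* Then define that day as day 0 for the 6-month primary endpoint, all visit windows and the adverse-event time points, including for patients who are not injected. Align Primary Endpoint, Data Collection, Patient Study Calendar and Time Period for Adverse Events with that definition.

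Patients not injected because of the aspirate remain in ITT as planned, so the change reduces untreated ITT participants without eliminating them.

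The cost is small. Allocation and drug preparation must always be done on the injection day, which the protocol already permits. Product is already supplied to the Orthopedic Center each day a consented or potential patient is seen there. No visit, product or sample size is added.

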**Study Enrollment Staggering**

In order to help ensure patient safety and to help limit unreasonable risk the first six subjects will be enrolled in staggered intervals. One subject may be enrolled per week for the first six subjects. Half of the six subjects will be randomized to pAF and the other half will be randomized to SOC steroid. Preliminary safety data for the first six subjects will be gathered and reviewed by the Data Safety and Monitoring Board (DSMB). If the DSMB expresses no concern over the preliminary data, the study may proceed with enrollment.

**Study Drug Administration**

Study Drug Administration will only occur at the Orthopedic Center. Patients that are screened and consented at participating sub-investigator clinics will need to go to the Orthopedic Center to receive study drug. Patient eligibility will be reviewed prior to study drug administration. The standard of care

**A Phase I/II Randomized, Double-Blinded Standard of Care (Corticosteroid vs Sterile Amniotic Fluid for Osteoarthritis**

**PI: [name].**

**Version: 5.00 dated 23MAY2023**

steroid injection includes corticosteroids (40mg/cc Kenolog, 2ml of Ropivacane [3mL total]). The amniotic fluid injection will also be given as 3mL of drug injected directly into the knee.

Frozen processed amniotic fluid will be provided in a validated container with dry ice, by the CTRM each day that a consented or potential patient is seen in the Orthopedic Center. If the patient has been randomized to receive the amniotic fluid injection, unblinded research staff will prepare the injection and place a blank label over the syringe to ensure the blind. The amniotic fluid will be room temperature (same as the steroid injection) prior to being given to the treating physician to further ensure the blind. The assignment of study drug will be randomly selected. Neither the patient, nor their providers will know what the patient is receiving.

Prior to the injection, aspiration of the knee may be indicated. The treating physician will perform the aspiration and the volume and characteristics of the aspiration will be recorded. After the aspiration is performed, the syringe is removed from the needle while the needle remains in place. The injectate is then screwed onto the same needle and its contents are injected into the knee per the standard of care. If no aspiration needed, then a 18g to 25g 1.5-inch needle is used to inject the injectate.

If the treating provider suspects an infection of the knee due to the appearance of the aspirate the aspirate will be sent for cultures and the patient will not receive a study drug injection. The subject will still be required to complete the follow up assessments as detailed in the patient study calendar per the intention to treat principle.

For the **Corticosteroid injection**, the skin is prepped with Chloraprep. The skin is anesthetized using a freezing spray. Then a mixture of 1 mL of Kenalog (corticosteroid) and 2 mL of ropivacaine is injected into intra-articular space of the knee.

For the processed **Amniotic Fluid injection**, the pAF injectate is prepared. The skin is prepped with Chloraprep. The skin is anesthetized using a freezing spray. 3 mLs of the pAF injectable solution is injected into the intra articular space of the knee.

Ultrasound guidance will be used for all study injections.

Following injection, patients will receive post injection strength training recommendations as determined by the treating PI and as the patient tolerates.

**Follow-up Visits/Emails/Phone Calls/Texts:**

The patient will have one (1) standard of care in-person clinic visit and five (5) follow up questionnaires /phone call visits as part of research. The patient may come to the clinic for an evaluation at any time if they are experiencing any pain or side effects as part of standard of care.

The schedule of follow up visits are:

- **24 hours:** Follow up phone call will be made 1 day after study drug injection. The phone call will be made to assess AEs. The study team will instruct the subject to contact the study team at any

**A Phase I/II Randomized, Double-Blinded Standard of Care (Corticosteroid vs Sterile Amniotic Fluid for Osteoarthritis**

**PI: [name].**

**Version: 5.00 dated 23MAY2023**

point if new or worsening AEs arise. The subject reserves the right to come back into clinic for an in-person visit per standard of care.

- **48 hours:** Follow up phone call will be made 2 days after study drug injection. The phone call will be made to assess AEs. The study team will instruct the subject to contact the study team at any point if new or worsening AEs arise. The subject reserves the right to come back into clinic for an in-person visit per standard of care.
- **1 month:** Follow up in-person clinic visit with associated physical exam and questionnaires. This visit is part standard of care. If the patient is unable to return to clinic, the patient may receive a phone call by the study team to do remote clinic visit and complete questionnaires.
- **3 Months:** Patient questionnaires sent by mail or email/text. If the patient is non-responsive to initial contact additional follow up contact (e.g. additional email/phone calls/text) will be made by the study team. The patient may receive additional follow up contact (e.g. email/phone call/text) by the study team to clarify any responses. The study team will instruct the subject to contact the study team at any point if new or worsening AEs arise. The subject reserves the right to come back into clinic for an in-person visit per standard of care. This is a study related follow up.
- **6 Months:** Patient questionnaires sent by mail or email/text. If the patient is non-responsive to initial contact additional follow up contact (e.g. additional email/phone calls/text) will be made by the study team. The patient may receive additional follow up contact (e.g. email/phone call/text) by the study team to clarify any responses. The study team will instruct the subject to contact the study team at any point if new or worsening AEs arise. The subject reserves the right to come back into clinic for an in-person visit per standard of care. This is a study related follow up.
- **12 Months:** Patient questionnaires sent by mail or email. If the patient is non-responsive to initial contact additional follow up contact (e.g. additional email/phone calls/text) will be made by the study team. The patient may receive additional follow up contact (e.g. email/phone call/text) by the study team to clarify any responses. The study team will instruct the subject to contact the study team at any point if new or worsening AEs arise. The subject reserves the right to come back into clinic for an in-person visit per standard of care. This is a study related follow up.

The patient may also receive additional phone calls by the study team to assess any adverse events that occur in between the scheduled 1-month follow-up visit and subsequent emails, phone calls, and/or text messages.

**A Phase I/II Randomized, Double-Blinded Standard of Care (Corticosteroid vs Sterile Amniotic Fluid for Osteoarthritis)**

**PI: [name].**

**Version: 5.00 dated 23MAY2023**

**PATIENT STUDY CALENDAR**

	Screening /Baseline	Day 1 (24± 5 hours post injection)	Day 2 (48 ± 5 hours post injection)	1-Month (± 1 week)	3-Months (± 2 weeks)	6-Months (± 1 month)	12-Months (± 1 month)	As needed
Eligibility A	X							
Informed Consent	X							
Medical History	X							
Concomitant Medications	X			X	X	X	X	X
Physical Exam	X			X				X
Laboratory tests B	x							
Randomization	X							
Study Drug Administration	X							
Follow-up Contact C		X	X	X D	X	X	X	X
In Person Follow-up Visit				X D				X
Pain Assessment E	X			X	X	X	X	
Outcome Assessment F	X			X	X	X	X	
Review of systems questionnaire G					X	X	X	
Review of adverse events H		X	X	X	X	X	X	X
Knee Aspiration I	X							
Aspiration Characteristics J	X							

B Laboratory tests include: PT/INR (only applicable to patients taking blood thinners) and urine hCG (only applicable to women of childbearing potential)

C Follow up Email/phone call/text may occur to clarify any responses and/ or assess AEs and/ or establish contact with the patient.

D The patient may receive a phone call by the study team to do remote clinic visit and complete questionnaires if the patient is unable to return to clinic to do in-person visit.

E Visual Analog Scale (VAS).

F Single Assessment Numerical Evaluation (SANE), PROMIS Physical Function CAT (PF CAT), and Knee Injury and Osteoarthritis Outcome Scale (KOOS). These surveys may be sent via email/text or done over the phone.

G This questionnaire may be sent via email/text or done over the phone.

H The study team may call the participant to assess adverse events in between the scheduled follow-up visit and phone calls.

I If deemed applicable by the treating provider.

J Only applicable if there is a suspicion of infection as determined by the treating provider.

**A Phase I/II Randomized, Double-Blinded Standard of Care (Corticosteroid vs Sterile Amniotic Fluid for Osteoarthritis**

**PI: [name].**

**Version: 5.00 dated 23MAY2023**

**WITHDRAWAL FROM STUDY**

A patient may withdraw from the study at any time, without a penalty or loss of benefits. Data collected up until the point of withdrawal will be still be used in efficacy and safety analyses.

Patients should not be withdrawn from the trial for AEs. Patients who discontinue the study will be followed for safety according to the safety monitoring plan and attempts to complete all safety assessments will be made, unless the subject withdraws consent.

**STUDY STOPPING/ DISCONTINUATION**

Events used to trigger discontinuation or stopping of the study pending a safety investigation include:

- If there is one death, irrespective of attribution
- If there is a SAE, that is possibly or probably related to study drug injection (pAf or steroid injection)
- Signs of severe hypersensitivity in a least 10% of enrolled patients
- If there is one case of hypersensitivity, defined as an acute inflammatory reaction requiring invasive intervention
- If there an adverse event that is classified as Severe per protocol that is possibly or probably related to the IP Injection (AF or steroid)

In the event study enrollment has been suspended due to the above criteria or any other reason the FDA, the DSMB, IRB and the Sponsor must be notified. Enrollment and treatment will be resumed after a review of the incident and of any corrective and preventive actions have been established with consultation between the study team, the Sponsor, and the DMSB. The study may not resume without FDA approval.

